5. GENERAL METHODOLOGY AND CONVENTIONS

5.1. Hypotheses and Decision Rules

5.1.1. Hypotheses and Sample Size Calculation

The planned sample size of the study is approximately 110 patients including approximately 9 patients in the Safety Lead-in, and approximately 100 patients in the Phase 2 portion of the study.

5.1.1.1. Safety Lead-in

There is no statistical hypothesis for the Safety Lead-in.

The primary endpoint of the Safety Lead-in is incidence of DLTs. Up to 9 evaluable patients will be enrolled to receive the high-dose encorafenib + binimetinib combination therapy. The safety and PK data will be evaluated by the Steering Committee after these 9 evaluable patients have been followed for a minimum of 28 days.

5.1.1.2. Phase 2

The sample size calculation is based on the primary endpoint of BMRR per mRECIST v1.1 by Investigator assessment. The study is designed to test the null hypothesis of $BMRR \leq 30\%$ for patients with *BRAFV600*-mutant melanoma brain metastasis, which is considered not sufficiently clinically meaningful to warrant further study. The alternative hypothesis is $BMRR > 30\%$ with the assumption that the true BMRR is at least 50%.

If the high-dose treatment is determined not to be safe in the Safety Lead-in, no patients will be enrolled into the high-dose treatment arm. Up to 100 eligible patients will be enrolled into 2 cohorts in the standard-dose treatment arm. Phase 2 enrollment will close when either Cohort 1 or 2 reaches the enrollment of 50 patients. The sample size consideration is based on an exact binomial test with a 1-sided alpha of 0.05 for each cohort.

- **Cohort 1:** Patients with locally confirmed *BRAFV600* cutaneous melanoma with metastases to the brain confirmed by MRI, asymptomatic, and *with* prior local therapy (eg, SRS or SRT).
- **Cohort 2:** Patients with locally confirmed *BRAFV600* cutaneous melanoma with metastases to the brain confirmed by MRI, asymptomatic, *without* prior local therapy (eg, SRS or SRT).

No formal statistical comparison will be conducted between the 2 cohorts.

5.1.2. Decision Rules

5.1.2.1. Safety Lead-in

The target DLT rate during Cycle 1 in the Safety Lead-in is $< 33\%$ (ie, < 3 out of 9 evaluable patients with DLTs). The high-dose treatment will be considered tolerable if the observed Cycle 1 DLT rate is $< 33\%$. [Table 2](#) provides a comparison of the characteristics of this DLT evaluation rule and the traditional 3 + 3 rules based on 9 patients.

Table 2: Characteristics of DLT Probability During the DLT Evaluation Period

True DLT Rate During DLT Evaluation Period	Probability of Dose Declared Toxic Using 3 + 3 Rules	Probability of Observed DLT Rate $\geq 33\%$ in 9 Patients During DLT Evaluation Period
10%	0.094	0.053
20%	0.291	0.262
30%	0.506	0.537
40%	0.691	0.768
50%	0.828	0.910

5.1.2.2. Phase 2

Under the assumption that the true BMRR $\geq 50\%$, the null hypothesis of BMRR $\leq 30\%$ will be rejected if at least 21 brain metastasis responses per mRECIST v1.1 are observed in a cohort of 50 patients. With approximately 50 eligible patients, the study will provide approximately 90% power with a 1-sided type I error rate of 5%.

5.2. General Methods

Unless otherwise specified, all analyses will be performed separately for the Safety Lead-in and for the Phase 2 portion of the study.

Qualitative/categorical data will be summarized by frequency counts and percentages. Percentages will be calculated using the number of patients in the relevant treatment arm or subgroup as the denominator. Continuous data will be summarized using appropriate descriptive statistics (eg, mean, standard deviation, median, minimum, and maximum) by treatment arm.

For reporting conventions, minimum and maximum values will be presented with the same decimal precision as collected in the raw data; mean, median, and quartiles should generally be presented to one more decimal place than the raw data; standard deviation should be displayed to two more decimal places than the raw data. Percentages will be reported to one decimal place. Unless otherwise noted, for all percentages, the number of patients in the analysis set for the treatment arm who have an observation will be the denominator.

Table summaries will be presented as follows. For Phase 2 portion of the study, patients in a cohort escalating to 600 mg encorafenib QD may also be summarized separately.

For Phase 2, the following analyses will be performed by cohort and overall (Cohort 1 + Cohort 2):

- Demographics and other baseline disease characteristics summary.
- Patient disposition.
- Protocol deviations.

- Efficacy analysis.
- Safety analysis.

The following analyses will be performed by cohort only:

- Study treatment exposure.
- Concomitant medication.
- Subsequent anticancer therapies/procedures.

Data listings will be sorted by cohort, patient identifier, parameter and the corresponding date of assessment. The listing source will be included in the footer of the listings.

Statistical analyses detailed in this SAP will be conducted using SAS[®], version 9.4 or higher (SAS Institute, Inc.). Noncompartmental PK analyses will be performed with Phoenix[®] WinNonlin[®] version 6.4 or higher (Certara USA, Inc., Princeton, NJ).

5.2.1. Data Handling After the Cut-off Date

Data after the cut-off date may not undergo the cleaning process and will not be displayed in any listings or used for summary statistics, statistical analyses or imputations.

All events with a start date before or on the cutoff date and an end date after the cutoff date will be considered as continuing at the cutoff date. The same rule will be applied to events starting before or on the cutoff date and not having a documented end date.

5.2.2. Analyses to Assess the Impact of COVID-19 Pandemic

The study enrollment occurs during the COVID-19 pandemic period. Therefore, the following data summaries and analyses may be performed to assess the impact of COVID-19 on the trial population and study data. Additional analyses may be added in a SAP amendment if they are considered necessary to evaluate the outcome of the trial. Details of these summaries and analyses are included in the respective sections.

- A listing of all patients affected by COVID-19 related study disruption.
- A listing of protocol deviations related to COVID-19.
- COVID-19 related AEs and deaths.
- Summary of missing tumor assessments due to COVID-19.

5.2.3. COVID-19 Anchor Date

If additional analyses are needed to assess the impact of COVID-19 on the trial population and the study data, an anchor date will be used as a start date for COVID-19 pandemic related periods based on Pfizer guidance and standard operating procedure (SOP):

- For global pandemic reference date: Use the date the World Health Organization designated COVID-19 as a global pandemic - March 11, 2020.
- For China reference date: Use the date COVID-19 was identified as the causative agent of outbreak in Wuhan by the China Center for Disease Control and Prevention - January 9, 2020.

When producing data summaries intended to show the potential impacts of COVID-19 on the study, data will be presented as “before” and “during,” where the anchor date is included in the “during” group.

A different anchor date may be used for purposes of regulatory submission should the regulatory authority requests.

5.2.4. Definition of Study Day

The study day for assessments occurring on or after the first dose of study treatment (eg, adverse event onset, laboratory date) will be calculated as:

$$\text{Study day} = \text{Date of the assessment/event} - \text{start date of study treatment} + 1.$$

The study day for assessments occurring prior to the first dose of study treatment (eg, baseline characteristics, medical history) will be negative and calculated as:

$$\text{Study day} = \text{Date of the assessment/event} - \text{start date of study treatment}.$$

The study day will be displayed in all relevant data listings.

5.2.5. On-treatment Period

On-treatment period is defined as the time from the first dose date of any study drug through (minimum of last dose of study treatment +30 days, start day of subsequent anticancer therapy - 1 day).

5.2.6. Date of Last Contact

The date of last contact will be derived for patients not known to have died at the data cutoff date using the latest complete date (ie, imputed dates will not be used in the derivation) among the following:

- All patient assessment dates (eg, blood draws (laboratory, Pharmacokinetics (PK)), vital signs, performance status, ECG, tumor assessments, hemodynamic assessment);
- Start and stop dates of concomitant therapies including non-drug treatments or procedures;

- Start and end dates of anticancer therapies administered after study treatment discontinuation including systemic therapy, radiation, and surgeries;
- AE start and end dates;
- Last date of contact collected on the survival follow-up electronic case report form (eCRF) (do not use date of survival follow-up assessment unless status is ‘alive’);
- Study treatment start and end dates;
- Date of discontinuation on disposition eCRF pages (do not use if reason for discontinuation is lost to follow-up or death).

Only dates associated with actual examinations of the patient will be used in the derivation. Dates associated with a technical operation unrelated to patient status such as the date a blood sample was processed or dates data were entered into the eCRF will not be used. Assessment dates after the data cutoff date will not be applied to derive the last contact date.

5.2.7. Unscheduled Assessments

Unless otherwise specified, unscheduled assessments will not be displayed in summary tables by nominal visit/timepoint. Unscheduled assessments will be used when deriving baseline and worst case on-treatment for safety analyses (except where noted for baseline ECGs). Additionally, unscheduled tumor assessments will be used for efficacy analyses (eg, defining date of progression/censoring, best overall response, date of last contact).

5.2.8. Tumor Assessment Date

If there are multiple scan dates associated with a tumor evaluation, ie, radiological assessments occur over a series of days rather than the same day, the earliest scan date associated with the evaluation will be used as the date of the assessment.

5.2.9. Adequate Baseline Tumor Assessment

An adequate baseline tumor assessment is defined as follows:

- Baseline assessments of all lesions (target, and non-target) must be within 28 days prior to or on the same day as date of first dose.
- All lesions (target and non-target) must have non-missing assessments.

Note: for target lesions, an actual measurement should be recorded and it should meet the criteria for being measurable and for non-target lesions the actual status at baseline should indicate that the lesion was present).

5.2.10. Adequate Post-baseline Tumor Assessment

An adequate post-baseline tumor assessment is defined as an assessment where a response of CR, PR, SD, non-CR/non-PD, or PD can be determined. Time points where the response is NE or no assessment was performed will not be used for determining the censoring date.

5.2.11. Standard Derivations and Reporting Conventions

The following conversion factors will be used to convert days into weeks, months or years:

1 week = 7 days, 1 month = 30.4375 days, 1 year = 365.25 days.

Percentages will be reported to one decimal place. The rounding will be performed to closest integer/first decimal using the common mid-point between the two consecutive values. Eg, 5.1 to 5.4 will be rounded to an integer of 5, and 5.5 to 5.9 will be rounded to an integer of 6.

5.2.12. Analyses for Binary and Categorical Endpoints

Binary and categorical endpoints will be summarized by frequency counts and percentages along with corresponding exact 2-sided Clopper-Pearson 95% CI. Unless otherwise specified, the calculation of proportions will include the missing category. Therefore counts of missing observations will be included in the denominator and presented as a separate category.

In case the analysis refers only to certain visits, percentages will be based on the number of patients with an assessment at that visit, unless otherwise specified.

5.2.13. Analyses for Continuous Endpoints

Continuous endpoints will be summarized using descriptive statistics ie, number of non-missing values and number of missing values [ie, n (missing)], mean, median, standard deviation, minimum, maximum and first and third quartile (Q1 and Q3). PK summaries will also include coefficient of variation percent (%CV).

In case the analysis refers only to certain visits, percentages will be based on the number of patients with an assessment at that visit, unless otherwise specified.

5.2.14. Analyses for Time-to-Event Endpoints

Time to event endpoints will be summarized using the Kaplan-Meier method¹ and estimated survival curves will be displayed graphically when appropriate. Graphs will describe the number of patients at risk over time. The median, quartiles, and probabilities of an event at particular points in time will be estimated by the Kaplan-Meier method. Confidence intervals for medians and quartiles are based on the Brookmeyer-Crowley method.² Confidence intervals for the estimated probability of event at a particular timepoint will be generated using the log(-log) method with back transformation to a confidence interval on the untransformed scale. Summaries of the number and percentages of patients with an event and reason for censoring will also be provided on summary tables and/or figures.

5.3. Methods to Manage Missing Data

Unless otherwise specified, all data will be evaluated as observed, and no imputation method for missing values will be used.

Any imputations will occur at the analysis dataset level. Additionally, in all patient data listings imputed values will be presented and flagged as imputed.

Missing statistics, eg, when they cannot be calculated, should be presented as ‘ND’ for not done, ‘NR’ for not reached or ‘NA’ for not applicable. For example, if N=1, the measure of variability cannot be computed and should be presented as ‘ND’ or ‘NA’.

5.3.1. Missing Dates

For purposes of data listings, dates will reflect only the information provided by the Investigator on the eCRF.

If start dates for adverse events or concomitant medications are completely missing a worst case approach will be taken whereby the events will be considered treatment emergent and the medications will be considered concomitant. If only partial information are available (eg, only a month and year or only a year) and the partial information provide sufficient information to indicate the dates are prior to the start of study treatment (eg, month/year less than month/year of first dose) then these will be considered to have started prior to treatment; otherwise a similar worst case approach will apply and these will be considered to have started after treatment.

Missing or Partial Death Dates

Missing or partial death dates will be imputed based on the last contact date:

- If the entire date is missing it will be imputed as the day after the date of last contact (see derivation of date of last contact in [Section 5.2.6](#)).
- If the day or month is missing, death will be imputed to the maximum of the full (non-imputed) day after the date of last contact and the following:
 - Missing day: 1st day of the month and year of death, or
 - Missing day and month: January 1st of the year of death.

Date of First and Last Dose of Study Treatment

No imputation will be done for first dose date.

Date of last dose of study drug, if unknown or partially unknown, will be imputed as follows:

- If the last date of study drug is completely missing and there is no End of Treatment eCRF page and no death date, the patient should be considered to be ongoing and use the cutoff date for the analysis as the last dosing date. **Note:** the study team should confirm that the patient is actively receiving dose at the time of the data cutoff.

- If the last date of study drug is completely or partially missing and there is EITHER an End of Treatment eCRF page OR a death date available (within the data cutoff date), then impute as follows:
 - If only Year is available and Year < Year of min (EOT date, death date), impute the date as 31DECYYYY.
 - If both Year and Month are available and Year = Year of min (EOT date, death date) and Month < Month of min (EOT date, death date), impute as last day of the month.
 - For all other cases, impute as min (EOT date, death date).

Date of Start of New Anticancer Therapy

Incomplete dates for start date of new anticancer therapy will be imputed as follows and will be used for determining censoring dates for efficacy analyses. PD date below refers to PD date by Investigator assessment. If the imputation results in an end date prior to the imputed start date then the imputed start date should be set to the end date.

- The end date of new anticancer therapy will be included in the imputations for start date of new anticancer therapy. If the end date of new anticancer therapy is:
 - completely missing then it will be ignored in the imputations below;
 - partially missing with only year (YYYY) available then the imputations below will consider 31DECYYYY as the end date of the new anticancer therapy;
 - partially missing with only month and year available then the imputations below will consider the last day of the month for MMMYYYY as the end date of the new anticancer therapy.
- For patients who have not discontinued study treatment at the analysis cut-off date, last dose of study treatment is set to the analysis cut-off date in the imputations below.
- If the start date of new anticancer therapy is completely or partially missing then the imputed start date of new anticancer therapy is derived as follows:
 - Start date of new anticancer therapy is completely missing.

Imputed start date = min [max(PD date +1, last dose of study treatment +1), end date of new anticancer therapy].
 - Only year (YYYY) for start of anticancer therapy is available.

IF YYYY < Year of min [max(PD date +1, last dose of study treatment +1), end date of new anticancer therapy] HEN imputed start date = 31DECYYYY;

ELSE IF YYYY = Year of min [max(PD date +1, last dose of study treatment +1), end date of new anticancer therapy];

THEN imputed start date = min [max(PD date +1, last dose of study treatment +1), end date of new anticancer therapy];

ELSE IF YYYY > Year of min [max(PD date +1, last dose of study treatment +1), end date of new anticancer therapy];

THEN imputed start date = 01JANYYYYY.

- Both Year (YYYY) and Month (MMM) for start of anticancer therapy are available

IF

YYYY = Year of min [max(PD date +1, last dose of study treatment +1), end date of new anticancer therapy], AND

MMM < Month of min [max(PD date +1 day, last dose of study treatment +1 day), end date of new anticancer therapy].

THEN

imputed start date = DAY (Last day of MMM) MMM YYYY;

ELSE IF

YYYY = Year of min [max(PD date +1, last dose of study treatment +1), end date of new anticancer therapy], AND

MMM = Month of min [max(PD date +1 day, last dose of study treatment +1 day), end date of new anticancer therapy]

THEN

imputed start date = min [max(PD date +1 day, last dose of study treatment +1 day), end date of new anticancer therapy];

ELSE IF

YYYY = Year of min [max(PD date +1, last dose of study treatment +1), end date of new anticancer therapy], AND

MMM > Month of min [max(PD date +1 day, last dose of study treatment +1 day), end date of new anticancer therapy].

THEN

imputed start date = 01 MMM YYYY;

ELSE IF

YYYY < Year of min [max(PD date +1, last dose of study treatment +1), end date of new anticancer therapy].

THEN

imputed start date = DAY (Last day of MMM) MMM YYYY;

ELSE IF

YYYY > Year of min [max(PD date +1, last dose of study treatment +1), end date of new anticancer therapy].

THEN

imputed start date = 01 MMM YYYY.

AE Dates

AE Onset Date:

If completely missing, the onset date will be set to first dose date if date of the first dose is less than AE stop date. Otherwise if date of the first dose is after AE stop date, then set the onset date to the earliest of non-missing AE stop date or informed consent date.

AE Stop Date:

If completely missing, the stop date will be imputed as the latest of the end of study date, death date, last dose date of the study treatment, or onset date.

Partial AE Date:

Partial AE date will be imputed based on the imputation rule for “Other Missing or Partial Dates”. If the AE onset date is imputed from a partial AE date and date of the first dose falls in the same month as the AE onset date, the following will be done:

- The AE onset date is reset to date of the first dose.

If AE stop date is imputed, and less than date of the first dose, set the AE stop date to date of the first dose.

Other Missing or Partial Dates

Imputation methods for other partial dates are as follows:

- If the day of the month is missing for a start date used in a calculation, the 1st of the month will be used to replace the missing date.
- If both the day and month are missing, the first day of the year is used.

- For stop dates, the last day of the month, or last day of the year is used if the day or day and month are missing, respectively.

These rules are used unless the calculations result in negative time durations (eg, date of resolution cannot be prior to date of onset). In these case, the resolution and onset dates will be the same and the duration will be set to 1 day.

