3.4.1. Adverse Events

An AE is considered a treatment-emergent adverse event (TEAE) if the event starts on or after the first dosing day and time/start time, if collected, but before the last dose +30 days, or start of subsequent anticancer *drug* therapy minus 1 day, whichever occurs first. Any events that started prior to date of the first dose are not considered TEAEs. If an AE starts on the same day as date of the first dose, it will be considered treatment emergent unless the CRF data indicates otherwise via explicitly recording time for AE onset and treatment dosing.

Adverse events will be coded using current Medical Dictionary for Regulatory Activities (MedDRA). Severity of AEs will be graded using the NCI-CTCAE v 4.03 toxicity grading scale.

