6.5.3. Study Treatment Exposure

Duration of Exposure

- **Intended treatment duration** (days) = end of treatment date – date of first dose of study drug +1.
 - If a patient permanently discontinues both binimetinib and encorafenib, end of treatment date is the date of last dose of the study drug;
 - If a patient permanently discontinues binimetinib but is still on single-agent encorafenib treatment, end of treatment date is the date of last dose of encorafenib treatment.
- **Actual treatment duration** (days) = date of last non-zero dose of the study drug - date of first dose of study drug +1

Cumulative Dose

Cumulative dose is defined as:

- **Intended cumulative dose** (mg) = sum of all protocol specified doses across intended treatment duration.
- **Actual cumulative dose** (mg) = sum of all actual doses that the patient received across actual treatment duration.

For patients who did not take any drug the actual cumulative dose is by definition equal to zero.

Dose Intensity

- **Intended dose intensity** (mg/day) = intended cumulative dose / intended treatment duration.
- **Actual dose intensity** (mg/day) = actual cumulative dose / intended treatment duration.
- **Relative dose intensity** (%) = $100 * (\text{actual dose intensity} / \text{intended dose intensity})$.

A summary of exposure, including duration of exposure, cumulative dose, actual dose intensity, and relative dose intensity (including categories <50%, 50%-<75%, 75%-<90%, 90%-<110%, and $\geq 110\%$, if applicable), will be presented for each study drug.

Actual treatment duration will be summarized in months including descriptive statistics (n, mean, median, minimum, maximum) and will also be categorized by time intervals (eg, <1 months, 1-3 months, etc. as appropriate for the protocol) for which frequency counts and percentages of patients will be provided.

Actual treatment duration, cumulative dose, actual dose intensity, and relative dose intensity will also be listed for each patient by treatment arm.

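### The rule for a partial last-dose date has no branch for a known month in an earlier year than the end-of-treatment or death date, so it imputes a date later than the recorded month allows

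*SAP*

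**What the plan says.** SAP 5.3.1, under the heading on first and last dose dates, sets three branches for a last-dose date that is wholly or partly missing when an End of Treatment page or a death date exists. Write R for the earlier of the end-of-treatment and death dates.

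1. Year only, earlier than R: "If only Year is available and Year < Year of min (EOT date, death date), impute the date as 31DECYYYY".
2. Year and month known: "If both Year and Month are available and Year = Year of min (EOT date, death date) and Month < Month of min" (end-of-treatment date, death date). The last day of the month is then imputed.
3. Everything else: "For all other cases, impute as min (EOT date, death date".

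Two other rules in the same section deal with a similar situation. For the start of new anticancer therapy with year and month known, there is a separate branch for "YYYY < Year of min [max(PD date +1, last dose of study treatment +1), end date of new anticancer therapy", and it imputes the last day of the recorded month. For other missing or partial dates there is a general rule, given here up to its closing words: "For stop dates, the last day of the month, or last day of the year is used if the day or day and month are". That general rule also keeps the recorded month, but it covers only dates that have no rule of their own.

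**The concern.** Branches 1 and 2 both stay within what the site recorded. A last dose with year and month known, in a year before R, meets neither: branch 1 needs the year to be the only information, and branch 2 needs the year to equal that of R. It drops to branch 3 and receives R, a date that the recorded month rules out.

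The last-dose date feeds several outputs:

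- On-treatment period (SAP 5.2.5), which ends at the "minimum of last dose of study treatment +30 days, start day of subsequent anticancer therapy - 1 day".
- Treatment-emergent adverse events (SAP 3.4.1), which must start on or after first dose "but before the last dose +30 days", or before subsequent anticancer drug therapy if that comes first.
- Actual treatment duration (SAP 6.5.3): "date of last non-zero dose of the study drug - date of first dose of study drug +1". Intended duration also ends at last dose and is the denominator of actual dose intensity.
- Deaths within 30 days after last dose (SAP 6.6.2). If R is the death date, the imputed last dose equals the death date and the patient is counted automatically, even where the recorded month excludes it.
- The imputed start of new anticancer therapy, through last dose plus 1 day (SAP 5.3.1), which is used for efficacy censoring.

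A last-dose date that is too late can therefore move events that occurred after treatment into the on-treatment summaries.

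**Working it through.** No figure in the plan needs reproducing, so the check is to apply the three branches literally. The calendar dates are illustrative assumptions, not trial data. The excess is the imputed date minus the last day of the recorded month. It is a lower bound, because the true last dose may have been earlier in that month.

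| Recorded last dose | R | Branch | SAP imputes | Latest date the record allows | Excess (days) |
|---|---|---|---|---|---|
| 2020 (year only) | 12 Jan 2021 | 1 | 31 Dec 2020 | 31 Dec 2020 | 0 |
| Dec 2020 | 12 Jan 2021 | 3 | 12 Jan 2021 | 31 Dec 2020 | 12 |
| Nov 2020 | 12 Jan 2021 | 3 | 12 Jan 2021 | 30 Nov 2020 | 31 + 12 = 43 |
| Oct 2021 | 15 Feb 2022 | 3 | 15 Feb 2022 | 31 Oct 2021 | 30 + 31 + 31 + 15 = 107 |
| Nov 2021 | 10 Dec 2021 | 2 | 30 Nov 2021 | 30 Nov 2021 | 0 |

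**General bound.** When branch 3 catches an earlier-year month, R is 1 January or later and the recorded month ends on 31 December or earlier. The excess is therefore always at least 1 day.

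**More information, worse answer.** With R = 12 January 2021, the year 2020 alone gives 31 December 2020. Adding that the month was November moves the imputed date later, to 12 January 2021. A deliberate conservative rule would not behave this way.

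**Safety window (last dose + 30 days), November 2020 case.** As written: 12 Jan 2021 + 30 = 11 Feb 2021. With the month respected: 30 Nov 2020 + 30 = 30 Dec 2020. The difference is again 43 days, unless subsequent therapy ends the window sooner.

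**Treatment duration.** Last dose minus first dose plus 1 rises by the same number of days as the excess. Actual dose intensity is actual cumulative dose divided by intended duration, so with recorded doses unchanged it falls.

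**How often.** Assume last doses are spread evenly over the year and R falls L days after last dose. The share crossing a year end is L/365: 7/365 = 1.9%, 14/365 = 3.8%, 30/365 = 8.2%. Only those that also lack the day are affected. The documents give no rate of day-missing last-dose dates. Assuming 1% to 5% among about 110 patients, the expected number is 110 × 0.01 × 0.019 = 0.02 to 110 × 0.05 × 0.082 = 0.45 patients.

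**The case against.** The gap is not in dispute; the case on the other side is that it hardly matters.

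- **Rarity.** The error needs a missing day, an end-of-treatment or death date, and a year end between the two. On the assumptions above, fewer than one patient is expected. Diaries are returned each cycle and compliance is reviewed at each visit (Protocol 6.1 and 6.4), the last-dose date goes into the eCRF (6.8) and source data are verified (9.8), so most partial dates should be resolved by query. This stands.
- **The 43-day example is near the long end.** The EOT visit window is ±7 days, and missing more than 28 consecutive days normally ends treatment, which suggests gaps of about 28 + 7 = 35 days. Longer gaps need an exception, a late visit or a death date only. This stands; the 12-day case is the more typical one.
- **Conditional effects.** The safety window is overstated only if subsequent therapy does not close it first. The imputed therapy start changes only if that date is also incomplete and last dose drives the formula. What is overwritten is a known month and year, not a complete date. All of this stands.
- **Primary endpoint.** Confirmed response under SAP 6.1.2 has no last-dose cut-off, so there is no direct effect. Protocol Appendix 5 does limit scans to 30 days after last dose, so an effect would arise only if that limit were applied, or indirectly through a later imputed therapy start.
- **Conservatism and transparency.** A longer window counts more events as treatment-emergent, and SAP 5.3 has imputed values flagged in listings. But the SAP gives no worst-case rationale for last dose, and the summaries use the imputed value whether or not it is flagged.

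**Conclusion.** The concern holds, as a minor drafting error. As written, the rule returns an impossible last-dose date for every record with a known month in a year before the end-of-treatment or death date. The excess is at least 1 day, and 12 and 43 days in the two year-end 2020 examples. The new-therapy rule in the same section contains the missing branch, which points to an omission rather than a choice.

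The consequences are limited to exposure and safety summaries in few patients, if any. With up to 50 patients per cohort, one misassigned death or adverse event would still move a reported rate by 1/50 = 2 percentage points. The conclusion that the branch is missing rests on the text alone. The sizes rest on the assumed dates, and the frequency on the assumed lag and the assumed rate of missing days.

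**What to change.** Add one branch to the last-dose rule in SAP 5.3.1, before the catch-all: if year and month are both available and the year is earlier than the year of the reference date (the earlier of the end-of-treatment and death dates), impute the last day of the recorded month. Equivalently, widen the second branch to any recorded year and month that precede the year and month of the reference date.

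The same-year case is unchanged: November 2021 with end of treatment on 10 December 2021 gives 30 November 2021 either way. The cost is one line in the SAP and one in the derivation program. No endpoint, hypothesis or data collection changes.
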